Osteoarthritis affects 40 million Americans and 15 million people in the United States suffer from degenerative arthritis of the knee. Unicondylar knee arthroplasty (UKA) was introduced as a treatment option for degenerative arthritis of the knee in the early 1970's[1]. The procedure initially yielded variable results and this unpredictability resulted in broadly low levels of usage[1]. Recent improvements in the surgical techniques and technology used for UKA have increased the effectiveness of this surgery. As the average age of the United States population increases, this surgical procedure will become even more common. It is estimated by the Millennium Research Group that there will be 55,100 unicompartmental knee procedures in 2010 and the compound annual growth rate from 2009 to 2014 will be 8.3%.

UKA can be viewed as an attractive alternative to total knee arthroplasty (TKA) assuming the patient's osteoarthritis has remained isolated in a single compartment. UKA is generally a less invasive procedure than TKA. Since the procedure is less invasive there is usually less blood loss; more cartilage, tissue, and bone is spared, which results in shorter recovery times than TKA. This procedure is attractive to adults who are interested in remaining active pain-free lifestyles as they age.

Medical Need:

The cost-effectiveness of healthcare interventions, especially new technology, is becoming essential. Comparing the procedural costs of robotic-assisted surgery and the outcomes of the patients versus TKA, the gold standard, will help substantiate whether robotic-assisted surgery from an economic

viewpoint is a cost-effective treatment. In addition the rehabilitation after knee replacement surgery is critical to achieving proper functional outcomes. Information pertaining to knee replacement post discharge costs has been limited. Due to the lack of studies and the continued growth in the number of knee arthroplasty surgeries it is imperative to track post discharge costs of all variables.

Specific Aim:

To document and compare the procedural and postoperative costs, recovery time, and outcomes of two procedure types:

- Robotic assisted unicompartmental knee arthroplasty
- Manual total knee arthroplasty

Methods Overview:

Objectives:

To quantify the procedural costs and clinical outcomes of knee replacement surgery.

- To quantify the costs associated with each type of discharge status of the patients (Home Care [HC], Skilled Nursing Facility [SNF], Inpatient Rehabilitation Unit)
- To compare clinical outcomes of the patients based on discharge status
- To report on postoperative length of stay for each type of knee arthroplasty
- To present the quality of adjusted life years of the patients using questionnaire EQ-5D
- To quantify the costs of postoperative medications prescribed to the patient during the rehabilitation period (name, refills, dosage, and manufacturer)
- To quantify the costs of postoperative therapy for the patients (facility and regimen)
- To quantify the indirect medical costs associated with DME (Walkers, Canes, etc.)
- To measure the increase in functional scores preoperatively and at the completion of physical therapy
- To compare the length of time for a patient to return to work
- To compare the length of time for the patient to return to driving

Endpoints:

- The costs related to each type of discharge status will be summarized per procedure type. The analgesic use, physical therapy, durable medical equipment, and postoperative visits will be used to calculate the total costs. The data will be tracked for 1 year.
- The clinical outcomes of the patients will be assessed using the Knee Society Score, KOOS, reduced WOMAC and Forgotten Joint Score. The results from these questionnaires may be compared preoperatively, postoperatively at 2 weeks, 6 weeks, 3 months, 6 months, and 1 year, depending on the surgeons regular post-operative visit schedule. The surveys will be reported by procedure type and by discharge type.
- The length of stay for each procedure type will be reported and compared.
- Each patient's quality of life will be assessed using the EQ-5D. It will be recorded preoperatively, postoperatively at 2 weeks, 6 weeks, 3 months, 6 months, and 1 year. These data will be compared by procedure type.
- The physical therapy regimen, number visits, and costs associated with each session will be recorded and reported on for each procedure type. Patients will be measured on how quickly they complete the physical therapy regimen prescribed.

- Durable medical equipment such as canes, walkers, etc. will be tracked. Each patient will record how long each device was used. The costs of each device will be obtained from the facility or manufacturer. The data will be compared per procedure type.
- Patients will be given a functional test by a physical therapist preoperatively to get an initial starting point. The physical therapist will create a regimen for the patient to complete post operatively with an end point that is reachable based on the starting point. The length of time associated with reaching the end point will be captured.
- Patient employment will be documented. In addition a patient's leave from work will be recorded which may include things such as; short-term disability, vacation, or unpaid leave from work. The patient's salary will be requested and used to track the cost of missed time. If a patient elects not to disclose salary his or her zip code will be requested in order to find the median salary per that area. Worker's compensation claims may or may not factor into rehabilitation adherence and recovery time and will therefore be excluded from this study.
- A patient's return to work and function at work will be logged. The information will be compared based on procedure type.
- The time it takes a patient to return to driving will be tracked. In addition if the knee replacement procedure was performed on the left leg or right leg will be documented because this could factor into time it takes to return to driving. The length of time to return to driving will be reported by procedure type.
- The procedural costs of the different type of knee replacement allocated into different cost centers. The charges, costs, and reimbursements will also be examined and the data be gathered from the hospital accounting software.

Inclusion Criteria:

Study Design Patients will be recruited into the study under the direction of one of the principal investigators or qualified team members during regularly scheduled clinic visits. All patients over 21 years of age who require knee replacement surgery will be asked to participate in the study. These patients will have failed non-operative management of their joint disease and are candidates for partial joint replacement because of pain and joint stiffness that interferes with their performance of normal daily activities.

- Age, 21-80 years
- Sex, males and females will be included
- BMI less than or equal to 39
- Stable health, the patient would be able to undergo surgery and participate in the follow-up program based on physical examination and medical history
- Patient is willing and able to cooperate in follow-up therapy at Rebound facilities
- Patient has stable and functional collateral ligaments
- Patient or patient's legal representative has signed the Informed Consent form
- Failed non-operative management of their joint disease
- Need to obtain pain relief and improved function
- Moderate or severe pain with either walking or at rest
- Diagnosed with osteoarthritis in one or more compartments of the knee and non-surgical treatment options have failed to provide relief for symptoms

- Patient exhibits preoperative radiographic evidence of joint degeneration that cannot be treated in non-operative fashion

Exclusion Criteria:

Patients will be excluded from study participation if they are cognitively unable to complete study health-related quality of life forms and pregnant women are also excluded from participation in this study.

- Patients who, in the opinion of the Investigator, have an existing condition that would compromise their participation and follow-up in the study
- Patients with pre-op flexion contracture greater than 10 degrees, overall flexion less than 115 degrees, and varus/valgus greater than 10 degrees
- Patient who is on workmen's compensation
- Patients who are on chronic long acting preoperative narcotic pain medication
- Patients with inflammatory polyarthritis
- Women who are pregnant
- Subjects who are known drug or alcohol abusers or with psychological disorders that could affect follow-up care or treatment outcomes
- Subjects who are currently involved in another clinical study with the exception to an outcomes study
- Patients with a pathology which, in the opinion of the Principal Investigator, will adversely affect healing
- A diagnosed systemic disease that would affect their welfare or the overall outcome of study (i.e. Paget's disease, renal osteodystrophy)
- Patients receiving an isolated patellofemoral UKA, lateral UKA, or bi-compartmental arthroplasty
- Patients with significant medical condition preventing a well-functioning contralateral knee

Risk/Benefits:

This is a minimal risk study which involves collection of data. The purpose of this study is for research purposes only. There is no direct benefit to the patient to participate in this study. The results of this research study may contribute to clinical research overall and may be published.

Study Enrollment Procedure:

The study investigator will evaluate the patients for study inclusion/exclusion at their perioperative consultation visit. The surgeon will describe the various surgical options that he believes to be appropriate for each individual patient. The patient and surgeon then will determine which prosthesis is most appropriate for their surgical procedure. Then the surgeon or his assistant will explain the study to the prospective participant. Prospective participants will be encouraged to ask questions regarding study participation. Once they are fully informed about the study, the interested patients will be asked to sign a consent form.

Evaluation to be used for Knee Replacement Patients:

At each clinic visit which coincides with a study interval (preoperative, 2 weeks postoperative, 6 weeks, 3 months, 6 months and 1 Year) the surgeon or qualified member of the study will

- Assess the function and range of motion of the knee joint
- Document any complications that may have occurred after surgery
- Complete a radiographic assessment of the operated knee post-operatively per surgeon standard of care.
- Complete the Knee Society Score in order to provide a rating of the pain, function, range of motion, and knee joint stability for each patient
- Study participants will be asked to complete standardized health-related quality of life instruments to document their perception of their pain and function. Study participants will complete the following outcome instruments. These instruments can be completed via phone, mail, website, or email if a clinic visit is not required at the study interval per surgeon standard of care.
 - a) The American Knee Society Score is subdivided into a knee score that rates only the knee joint itself and a functional score that rates the patient's ability to walk and climb stairs[2].
 - b) The EQ-5D is a standardized instrument for use as a measure of health outcome. Patients will be also given a questionnaire with questions pertaining to employment, loss of wages, driving, etc.
 - c) The Reduced WOMAC is a truncated version of the Western Ontario and McMasters University Osteoarthritis Index. The questionnaire is patient administered and designed to assess pain, disability and joint stiffness in the OA patient[3].
 - d) The KOOS or Knee injury and Osteoarthritis Outcome Score is a patient completed questionnaire to assess the patient's opinion regarding their knee and its associated OA. Poor outcomes are reported with a lower score and good outcomes with a higher score [4-7].
 - e) Post-op, the Forgotten Joint Score is a 12-item questionnaire completed by the patient to determine how aware they are of their joint in their everyday life[8].
- Post-op patients will complete a “progress report” regarding their satisfaction and rehabilitation.
- At 6 weeks post-op, patients will also be asked to complete a “return to function” questionnaire regarding their rehabilitation including their return to work and driving and physical therapy regimen. This questionnaire can be completed via phone, mail, website or email if a clinic visit is not required per surgeon standard of care.

In addition to regularly prescribed physical therapy, patients will meet with a physical therapist or qualified member of the study preoperatively for testing to create a starting point. They will also undergo multiple tests/ measurements at 6 weeks and 3-months postoperatively. The physical therapist will create a physical therapy regimen and create an endpoint for the patient. The endpoint will be goals within reach for each patient to complete before the patient can discontinue physical therapy.

- The patient will undergo a series of tests to create an initial starting point preoperatively and post operatively at 6 weeks and 3 months. The tests will be the following:
 - Timed up and Go (TUG) Test: Participants are instructed to stand up from a seated position from a standard chair, walk 3m around a cone and then return to the chair and resume a seated position. Pace is self-selected. The time to complete the test is recorded.

- 6 Minute Walk Test (6MWT) : Participants are instructed to cover as much distance walking in 6 minutes and can stop and rest if necessary. The course is 30 meters in length, marked at 1 meter intervals with cones marking the turnaround point. Distance measured is rounded up to the nearest meter and recorded.
 - Stair Ascend/Descend Test: Participants are asked to ascend and descend 11 steps using a hand rail if necessary. Stair height is 17.8 cm (7"). Pace is self-selected. The time to ascend/ descend 1 flight of stairs is recorded.

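### The 1-year cost comparison of robotic UKA with manual TKA does not price the hospital cost of a readmission, reoperation, revision or conversion

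*Combined protocol and SAP*

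**What the plan says.** The economic purpose is stated under Medical Need: the comparison with TKA "will help substantiate whether robotic-assisted surgery from an economic" viewpoint is cost-effective. The same section holds that "it is imperative to track post discharge costs of all variables". The Specific Aim is "To document and compare the procedural and postoperative costs, recovery time, and outcomes of two procedure types", namely robotic-assisted UKA and manual TKA.

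The first Endpoints bullet defines the post-discharge total: "The analgesic use, physical therapy, durable medical equipment, and postoperative visits will be used to calculate the total costs". It then sets the window: "The data will be tracked for 1 year". Other Endpoints bullets cover lost work (valued from salary, or from the area median) and the procedural cost of the knee replacement by cost centre. The Objectives add costs by discharge destination and include "To present the quality of adjusted life years of the patients using questionnaire EQ-5D".

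Cost Data names the sources: each facility's cost accounting system, with CPT codes and the 2010 Medicare Fee Schedule as fallback.

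Adverse events appear as a clinical task. At each clinic visit that falls on a study interval, the surgeon or a team member is to "Document any complications that may have occurred after surgery". No section attaches a cost to what is documented.

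**The concern.** A cost comparison between two operations should count what it costs when either one fails. Within the first year the expensive failures are those that return the patient to hospital: a readmission, a reoperation, a revision, or the conversion of a UKA to a TKA. None of these is listed as an endpoint, an event or a cost item. The items that are listed describe the normal course of recovery.

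If the total-cost definition is followed as written, two patients with the same recovery costs could show much the same total even though one was operated on twice. If such events are not equally frequent and equally costly in the two arms, the difference in mean cost is biased by the omitted amount. That difference is one half of the economic statement the study is meant to support; the EQ-5D result is the other.

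**Working it through.** The documents state no sample size, power, event rate or event cost, so there is no figure to reproduce. The check is a reading of every cost item, followed by two illustrations whose inputs are assumptions.

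**Step 1. Does any cost item pick up the hospital cost of a failure?**

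- Endpoints, first bullet: four named components. Hospital admission and repeat surgery are not among them.
- Objectives and Endpoints, discharge status: the cost of home care, skilled nursing or inpatient rehabilitation, tied to the type of discharge. A later admission is not mentioned.
- Endpoints, employment: cost of missed work. This would register some of the effect of a second operation, but not its hospital cost.
- Endpoints, procedural cost: the knee replacement itself, by cost centre, from hospital accounting software. Repeat surgery is not mentioned.
- Cost Data: this names sources, not further items. The accounts may hold readmission charges, but nothing says they will be extracted or added to the total.

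So the hospital cost of a failure is not priced anywhere. Its consequences (more visits, therapy, analgesics, equipment and lost work) fall under listed items and may be partly counted.

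**Step 2. Would the clinical record identify the events?** Only in part. Complications are recorded at clinic visits. Patient Follow-up schedules visits at 2 and 6 weeks, but makes those at 3 months, 6 months and 1 year optional, according to the surgeon's practice. Where no visit is needed, the outcome instruments may be completed remotely, but that route is not described for complications. The Time and Events Chart has no complications row. An event after 6 weeks could go unrecorded.

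**Step 3. How large could the omission be? (all inputs assumed)**

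Omitted difference in mean cost per patient, as a share of index-procedure cost = d × r, where d is the between-arm difference in 1-year failure rate and r is the cost of a failure relative to the index procedure. Assume d from 0 to 5 percentage points and r from 0.5 to 2.

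- d = 0: 0%
- d = 0.01, r = 0.5: 0.01 × 0.5 = 0.5%
- d = 0.02, r = 1.0: 0.02 × 1.0 = 2%
- d = 0.05, r = 2.0: 0.05 × 2.0 = 10%

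The formula uses one r for both arms. Converting a UKA and revising a TKA need not cost the same. The sign of d is unknown, so the range of 0% to 10% applies in either direction.

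**Step 4. How precisely would the added cost be estimated? (n and p assumed)**

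Expected events in an arm = n × p. Chance of none = (1 − p)^n.

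| n per arm | p | Expected events | Chance of none |
|---|---|---|---|
| 50 | 1% | 0.5 | 0.605 |
| 50 | 2% | 1 | 0.364 |
| 100 | 1% | 1 | 0.366 |
| 100 | 2% | 2 | 0.133 |
| 200 | 1% | 2 | 0.134 |
| 200 | 2% | 4 | 0.018 |

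At rates of this order, pricing the events removes a defect in the definition of cost but gives an imprecise estimate of their contribution.

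**The case against.** The strongest reply has four parts.

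- **The economic claim is modest.** The wording is that the comparison will help substantiate cost-effectiveness. The Specific Aim is to document and compare, the Data Analysis section is descriptive, and no incremental ratio is specified. A reader might infer that the plan sets out to settle cost-effectiveness over the life of the implant, but the documents do not say so. This part stands, and it limits the point to the 1-year comparison.
- **The horizon is visible.** The 1-year window is given under Endpoints and again under Timeline. This stands as well, so stating it in the economic conclusion is a clarification and not the repair of an error.
- **Failures are not cost-free.** A reader might infer that an arm with more early reoperations would look no more expensive. That is wrong: a second operation generates further visits, therapy, analgesics, equipment and lost work, all of which are listed. What is missing is the hospital cost of the event.
- **The omission may be loose drafting.** The call for all post-discharge costs, together with the use of facility accounts, could be read as covering readmissions. It is only a general statement of need. The sentence that defines the total names four components, and an analyst would follow that sentence.

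A reader might also infer that the omission favours UKA, since the background says of UKA in its early years: "The procedure initially yielded variable results and this unpredictability resulted in broadly low levels of usage". The same paragraph goes on to say that newer techniques and technology have made the surgery more effective, and no revision rate is given for either procedure. The documents do not support a direction.

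**Conclusion.** The concern holds for the definition of cost within the 1-year window. As written, the comparison omits the main direct cost of early failures while possibly counting some of their knock-on costs. It also falls short of the plan's own call to track post-discharge costs in full.

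Neither the size nor the direction of the bias can be derived from the documents. The 0% to 10% of index-procedure cost shown above rests wholly on assumed failure-rate differences and cost ratios, and includes no effect at all.

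The documents also do not support a statement about how much later revision would cancel a 1-year saving. They give no costs, and they do not establish that UKA is cheaper at 1 year.

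The plan should be corrected on this point before the cost analysis. The rest of the data collection can stand.

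**What to change.** 1. Amend the total-cost sentence under Endpoints to include all-cause readmissions and any reoperation, revision or conversion of the study knee within 1 year. Price them from the facility accounting system, or from the CPT and Medicare fallback, as Cost Data already provides.
2. Query the accounting system for every patient at 1 year, not only for those with a recorded complication. Add a short question on hospital admission and further knee surgery to the 3-month, 6-month and 1-year questionnaires that can be completed remotely.
3. In Medical Need and the Specific Aim, describe the economic conclusion as 1-year cost and outcome, and state that implant survival beyond 1 year is not assessed.

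The cost is a small extra data pull, one added question at three time points and some protocol wording. No visits or patients are added. Three drawbacks remain: the added cost component will be imprecise because events will be few, events treated at outside facilities will be captured incompletely, and the claim becomes narrower.

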Financial data will be obtained from each facilities cost accounting system. If data cannot be attained using this method, CPT codes will be recorded and cross-referenced with the 2010 Medicare Fee Schedule. The financial data will be estimated using this method. The use of Medicare reimbursement rate is reasonable given that more than 60% of arthroplasty cases are reimbursed by this agency. A patient's analgesic use will be recorded by the surgeon and the Average Wholesale Price will be assigned to each script. Discharge data collected in this study will be compared to 2006 National Hospital Discharge Survey (NHDS).

Data Management:

All data will be collected using data collection forms or questionnaires in clinic or via phone, mail, website or email. The data dependent upon the questionnaire or form will be recorded by the patient, investigator, or qualified team member. Information will then be entered into a secure online data entry system by a qualified team member and the data will be stored in a secure database. Numerous business rules ensure that only properly formatted data is submitted. The information undergoes further verification by a human operator, who checks the integrity of each record prior to submitting it to the database. All access to the information- including reports, queries and data tools- is password protected and restricted to users that have the proper credentials. Information pertaining to cost data will be uploaded separately into the database.

Data Analysis:

Descriptive statistics consisting of frequency tables and percent for categorical variables and means, standard deviations, and ranges for continuous variables will be tabulated at the conclusion of the study.

General Statistical Considerations:

Tabulation of summary statistics, graphical presentations, and statistical analyses will be performed using SAS® software. The primary presentations and analyses will be based on data pooled across study centers. Relevant summaries for individual centers, or combinations of centers, may be presented for primary data. All patient data will be presented in separate data listings. All patients who are enrolled in this study and receive any of the treatments as part of this study will be included in the safety analysis. All testing and confidence intervals will use a 0.05 significance level. All testing is two sided unless otherwise noted.

Patient Characteristics:

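### The 1-year total cost by discharge status is built from four inputs, and nothing adds the cost of the post-discharge setting itself

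*Combined protocol and SAP*

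**What the plan says.** The Objectives section includes: "To quantify the costs associated with each type of discharge status of the patients (Home Care [HC], Skilled Nursing Facility [SNF], Inpatient Rehabilitation Unit". A separate objective covers therapy: "To quantify the costs of postoperative therapy for the patients (facility and regimen".

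The first bullet under Endpoints serves the discharge-status objective. It opens with "The costs related to each type of discharge status will be summarized per procedure type" and continues with "The analgesic use, physical therapy, durable medical equipment, and postoperative visits will be used to calculate the total costs". The tracking period is 1 year.

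Pricing is described in several places:

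- Physical therapy (Endpoints): "The physical therapy regimen, number visits, and costs associated with each session will be recorded and reported on for each procedure type".
- Durable medical equipment, DME (Endpoints): "The costs of each device will be obtained from the facility or manufacturer".
- Analgesics (Cost Data): "the Average Wholesale Price will be assigned to each script".
- General source (Cost Data): facility cost accounting systems, with CPT codes and the 2010 Medicare Fee Schedule as fallback.

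Cost Data also plans to compare discharge data with the 2006 National Hospital Discharge Survey. Procedural cost is a separate endpoint, taken from hospital accounting software.

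**The concern.** The objective asks what each discharge status costs. The only sentence that says how the total is calculated lists items a patient may use after any kind of discharge, and leaves out the setting that defines the discharge status. An analyst following it would produce four-item totals stratified by discharge group. Such a table shows how much therapy, medication, equipment and follow-up each group used. It does not show what a nursing-facility or rehabilitation-unit discharge costs.

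Two results are at stake. One is the cost contrast between discharge settings, which is the objective itself. The other is the postoperative cost comparison between robotic UKA and manual TKA in the Specific Aim. The Medical Need section justifies the study by the scarcity of post-discharge cost data and says that all such costs should be tracked, which is broader than the four-item list.

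**Working it through.** The plan states no cost figure, so there is none to reproduce. The check is a comparison of texts, followed by algebra for what is left out.

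**Step 1: objective against sum.** The objective names 3 settings. The sum has 4 inputs: analgesics, physical therapy, DME and postoperative visits. Of the 3 settings, 0 appear in the sum.

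**Step 2: could an input carry the setting's cost under another name?**

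- Analgesics are priced per script, therapy per session and DME per device. So 3 of the 4 inputs have a stated unit, and none is per facility day or per home-care episode.
- Postoperative visits have no stated unit. Patient Follow-up uses the term for assessments by the surgeon or study team, which points to clinic visits but does not settle what the cost item covers.
- The therapy objective mentions the facility. At most this brings in therapy delivered there, not the rest of a stay.

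**Step 3: does another section add it?**

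- Cost Data names sources, not components of the total. It uses discharge data only for the external survey comparison.
- The length-of-stay endpoint is reported by procedure type and is not linked to a cost.
- The procedural-cost endpoint concerns the operation.
- The Time and Events Chart has no row for discharge destination, facility days or home-care use.

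**Step 4: what is omitted.** For setting s (home care HC, SNF, inpatient rehabilitation unit IRU), let p_s be the share of patients, E_s the mean episode cost, and V_s the therapy, drugs and visits inside E_s that the four inputs already count. The net omitted cost is N_s = E_s − V_s.

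- Within one discharge group: N_s per patient. The SNF versus home-care contrast therefore lacks the whole of N_SNF − N_HC, whatever the mix.
- Within one procedure: the sum over s of p_s × N_s.
- UKA minus TKA: the sum over s of (pUKA_s × NUKA_s − pTKA_s × NTKA_s).
- With equal N_s under both procedures, this becomes the sum of dp_s × N_s, where dp_s = pUKA_s − pTKA_s. For one point moved from home care to SNF, dp_HC = −0.01 and dp_SNF = +0.01, which gives 0.01 × (N_SNF − N_HC).

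**Range.** If home care is almost entirely therapy and visits, N_HC is near 0 and the one-point figure approaches 0.01 × N_SNF. If N_HC equals N_SNF, it is 0. If mix and net cost are the same for both procedures, the UKA−TKA difference is unaffected and only the level is too low. The documents supply no E_s, V_s or p_s, so no dollar value follows.

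**The case against.** The strongest reply is that the bullet is ambiguous rather than deficient. Its opening sentence already promises costs by discharge status, and the four-item sentence contains no word such as only. On one reading, setting costs come in under the opening sentence and the four items are further inputs. On another, the objective means downstream costs split by discharge group, for which four items would be a coherent definition.

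Part of this stands. A reader might infer that the plan deliberately excludes setting costs, and the text does not say that. But the first reading needs a fifth input that no section supplies. The second gives costs within discharge groups and leaves the cost of the status itself unmeasured.

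It can also be said that Cost Data refers to the accounting systems of facilities generally, while procedural cost is tied to the hospital's, so post-acute facilities may be meant. That is possible, but a source does not put an item into a sum.

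The objection is strongest for home care. A reader might infer that all three episodes are missing in full. Therapy and visits may be much of a home-care episode, so the omission there is partial and could be small. The gap is clear for SNF and rehabilitation-unit stays.

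Finally, materiality is not shown: there are no unit costs or discharge mix, and the procedure difference could be untouched. That limits what can be claimed about size, but not about the mismatch between objective and endpoint.

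**Conclusion.** The point holds as an omission in the endpoint definition. Followed as written, the 1-year total leaves out the SNF or rehabilitation-unit stay and any home-care cost not already counted. The post-discharge cost level is understated. The UKA−TKA difference is off by the weighted sum in Step 4, which is nonzero when mix or net episode cost differs between procedures, unless the terms cancel. Procedural cost, reported separately, is unaffected.

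This rests on reading the four-item sentence as the calculation rule and on net episode costs above zero. It should be fixed, but it does not invalidate the study.

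Two stronger inferences are not supported. One is that the comparison is biased towards a particular procedure: the expectation of quicker recovery after UKA, stated in the background, is a reason not to assume equal discharge mix, but it gives neither a mix nor a price. The other is that unpriced readmissions or reoperations belong to the same gap. That question would rest on the Specific Aim's mention of postoperative costs, not on the discharge-status objective, and is no part of this point.

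**What to change.** Replace the four-item sentence with a definition along these lines:

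*1-year post-discharge total cost per patient = analgesics + physical therapy + DME + postoperative visits + home-care, SNF or inpatient-rehabilitation episode cost, with therapy, drugs or visits already inside an episode price counted once.*

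Report it by procedure type and by discharge type, and keep procedural cost as its own endpoint.

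Two supporting changes are needed:

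- **Data.** Record discharge destination, and days in a facility or number of home-care visits, on an existing form. Discharge type is already required, since for the questionnaires "The surveys will be reported by procedure type and by discharge type". The amount of facility or home-care use is not listed in the chart, and could be hard to recover later.
- **Prices.** Name a source for facility days and home-care episodes where accounting data cannot be obtained. The CPT and fee-schedule fallback, as written, names no such price.

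The cost is one or two added data fields and some extra cost abstraction, with no added patient visits. If the sponsor intends to leave setting costs out, the endpoint should say so with a reason, and the objective should be narrowed to match.
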